13.2 Minimizing coercion or undue influence

The reimbursements for participation have been set in line with the local economy and recent research studies conducted with this population and will only compensate participants for their time in completing the questionnaires. The Enrollment Consent Form specifies the reimbursement amounts in the local currency, VND.

13.3 Description of risks

This study poses no more than minimal risk to participants. The active ingredient in CSD500 can cause headaches, faintness and nausea, loss of sensation, dizziness and skin irritation (see Package Insert). Participants will be instructed to stop using the study condoms if either they or their partner experience any of these symptoms and will be referred for standard care, as indicated.

Participants may experience psychological risks associated with answering questions about sensitive topics or reporting attitudes and behaviors, such as their sexual activity and details of their sexual relationships. Several measures have been implemented to minimize these risks. First, during the consent process, participants will be advised that they are free to decline study participation. Participants also will be informed that they can decline to answer any questions. Participants also will be informed of their freedom to terminate the interview or visit at any time. All interviews that take place in-person will occur in a private setting by interviewers who have been trained thoroughly on the importance of confidentiality, the procedures to protect a participant's confidentiality, and the penalties associated with breaches of confidentiality.

Participants' personal information will be kept confidential. Access to the signed consent forms and the Participant Identification Log (i.e., the roster linking participant names and PINs) will be limited to authorized study personnel and remained locked in a file cabinet when not in use.

We will not perform any genetic testing.

13.4 Description of anticipated benefits to the research participant

There are no study benefits to the research participant. Participants and others may indirectly benefit in the future from the trial results.

13.5 Description of potential risk to anticipated benefit ratio

The potential risks involved in trial participation are reasonable in relation to the anticipated benefits.

13.6 Provisions for protecting privacy and confidentiality

Participants' privacy and the confidentiality of data will be protected through training of interviewers and other study staff; conducting all interviewing, and physical examinations in private; storing study materials in a locked room; and securing computer files that include identifiers. Only the study PINs will identify participant research records. Linkages between PINs and participants' identifying information will not be maintained in a computer database; rather, they will be maintained in a paper log that is kept locked and only accessible to study staff at the study site. These linkages will be destroyed at an agreed upon timeframe after the main study articles are published. Data identifying individual study participants will not be published or released to persons outside of the project.

13.7 Treatment and compensation for injury

No money has been set aside for compensation for injury from study participation; however, this study poses no more than minimal risk to participants.

13.8 Data and Safety Monitoring Committee (DSMC)

The Regulatory and Ethics Core of the CCTS at OSU will assemble a Data Safety Monitoring Committee (DSMC) – consisting at minimum of a research ethicist / research subject advocate, biostatistician, and gynecologist – to independently monitor the safety of the study. The DSMC will review 1) the protocol before the accrual of human subjects; and the accumulated data after 2) approximately 50-100 women-months of follow up have been completed; 3) after approximately half of the expected women-months have been accrued; and 4) after study follow-up has ended. The DSMC will evaluate participant safety and study conduct and progress and will make recommendations to the sponsor and investigators concerning the trial continuation, modification or termination. No specific stopping guidelines will be presented with the data, and recommendations for stopping early for safety reasons will be based on the judgment of the DSMC. The Committee will approve a detailed DSMC plan before the accrual of human subjects.

14. PLANS FOR REPORTING RESULTS

Upon completion of data analyses, the Site Investigator will organize the dissemination of the main study findings to the study team in Vietnam as well as to local stakeholders. In addition, the primary results will be written up for publication in a peer-reviewed scientific journal. Additional papers will also be written and submitted to peer-reviewed scientific journals as appropriate.

A publication policy will be established to govern the publication of the results of the trial. Authorship roles will be assigned primarily according to the contributions of individual members as well as the likelihood that the authors will be able to complete data analysis and preparation of manuscripts in a timely manner. All investigators will be encouraged to participate in the discussions regarding authorship. All abstracts and publications resulting from this study must be cleared and approved by all participating institutions prior to submission to scientific meetings or journals.

16. ATTACHMENTS

1. Study timeline
2. Schedule of study procedures
3. Futura Max package insert
4. Futura Max packaging design
5. Recruitment Script
6. Counseling Checklist
 - Control Arm
 - Intervention Arm
7. Futura Max Information Sheet
8. Letters of support
 - [name] [name]
 - [name] [name], PhD
 - [name]
9. Data Safety and Monitoring Committee Charter
10. Data collection forms
 - Eligibility Assessment Form
 - Randomization Assignment Form
 - Vaginal Swab Collection Form
 - Female Enrollment Questionnaire
 - Male Enrollment Questionnaire
 - Female Follow-up Questionnaire
 - Male Follow-up Questionnaire
 - Study Discontinuation Form
 - Interim Visit Form
 - Adverse Event Form
11. Enrollment Consent Form
12. Annotated Enrollment Consent Form

Study timeline

Schedule of study procedures

Study procedure	Visit				
	Enroll- ment	2-month	4-month	6-month	Interim
Participant identification number (PIN) assigned	♀				
Eligibility Assessment Form	♀				
Enrollment Consent Form	♀				
Randomization Assignment Form	♀				
Female Enrollment Questionnaire	♀				
Male Enrollment Questionnaire	♂				
Condom counseling	♀ ^a	♀ ^a	♀ ^a	♀	
Condom provision	♀ ^a	♀ ^a	♀ ^a	♀	†
Provide Futura Max Information Sheet	♀ ^a	♀ ^a	♀ ^a		
Vaginal swab collection and Form	♀	♀	♀	♀	
Female Follow-up Questionnaire		♀	♀	♀	
Male Follow-up Questionnaire				♂	
Study Discontinuation Form	†	†	†	†	†
Interim Visit Form					†
Adverse Event Form	†	†	†	†	†
Obtain contact information	♀	♀	♀		
Participant compensation	♀	♀	♀	♀	

Procedure completed by couple (♀); woman only (♀); man only (♂); only if needed (†)

^aAccording to randomized arm assignment

VN CSD500 Study
Counseling Checklist: Control Arm

1. Greets patient respectfully.

- Assures privacy.
- Tries to put at ease if shy or embarrassed.

2. Asks what patient knows about condoms and about past experience with condoms.

- Corrects any myths or incorrect information.

3. Provides basic facts about condoms.

- Explains that condoms provide a barrier to 1) protect man and woman against spread of HIV and other sexually transmitted infections and 2) woman against pregnancy.
- Counsels talking with partner about using condoms.
- Asks if has any questions and answers them.

4. Provides specific instruction on how to correctly use and when to use condoms.

- Couple should use during every act of intercourse.
- Couple should not "test" condoms by blowing up or unrolling.
- Condom should be put on when penis is erect.
- Condom should be put on before the penis comes near or is put into the vagina.

5. **Demonstrates** how to correctly put on condom by using a model, banana, or two fingers.

- Cautions **not to unroll** condom before putting on.
- Shows how to place condom rim on penis and how to unroll up to penis base.
- Instructs on how to leave 1/2 inch space for semen at tip of condom, which must not be filled with air or it may burst.
- Shows how to expel air by pinching tip of condom as it is put on.
- Cautions about tearing accidentally with fingernails or rings.

6. Counsels about what to do if condom breaks or slips off during sex.

- Woman should return to clinic to be assessed for emergency contraception.
- Woman should request emergency contraceptive pills within 72 hours (the earlier the better) of unprotected sex or breakage of a condom.

7. Has patient demonstrate and practice putting on condom using the model, banana or fingers.

- Corrects any technique errors.

8. Counsels patient on how to remove penis from vagina with condom intact and without spilling semen.

- Hold on to rim of condom when withdrawing.

- Be careful not to let semen spill into vagina when penis is flaccid.

9. Discusses use of lubricants and what not to use.

- Do not use any of these: petroleum-based products (e.g., Vaseline); mineral, vegetable, or cooking oil; baby oil; margarine or butter.

10. Advises to use a spermicide or water-based lubricant if one is needed.

11. Advises patient to dispose of condoms by burning, burying, or throwing in the latrine.

12. Repeats main condom messages to patient.

- Be sure to have condom on hand before you need it.
- Use a condom with every act of intercourse.
- Do not use a single condom more than once.
- Do not rely on condom if package is damaged, torn, outdated, dry, brittle or sticky.

13. Provides patient with condoms for two months.

- Multiply patient's expected weekly coital frequency by 9. Give her this number of condoms or, if this number is less than 20, give her 20 condoms.

14. Instructs patient not to share study condoms with anyone but main partner.

- Do not share study condoms with family or friends.

15. Reassures patient that should return at any time for advice or more condoms.

VN CSD500 Study
Counseling Checklist: Intervention Arm

1. Greets patient respectfully.

- Assures privacy.
- Tries to put at ease if shy or embarrassed.

2. Asks what patient knows about condoms and about past experience with condoms.

- Corrects any myths or incorrect information.

3. Provides basic facts about condoms.

- Briefly mentions that condoms protect against pregnancy and HIV and other sexually transmitted infections.
- **Explains that patient is receiving the new Futura Max condom. Futura Max condoms have a small amount of a special gel inside of the condom. This gel increases blood flow within the man's penis. This makes the man's erection harder and last longer. This can make sex an intense and more pleasurable experience for the couple.**
- Counsels talking with partner about using Futura Max condoms.
- Asks if has any questions and answers them.

4. Provides specific instruction on how to correctly use and when to use condoms.

- Couple should use during every act of intercourse.
- Couple should not "test" condoms by blowing up or unrolling.
- Condom should be put on when penis is erect.
- Condom should be put on before the penis comes near or is put into the vagina.
- Couple should not use more than one Futura Max condom within 24 hours. If having sex again within 24 hours, use a standard condom.

5. **Demonstrates** how to correctly put on condom by using a model, banana, or two fingers.

- Cautions **not to unroll** condom before putting on.
- Shows how to place condom rim on penis and how to unroll up to penis base.
- Instructs on how to leave 1/2 inch space for semen at tip of condom, which must not be filled with air or it may burst.
- Shows how to expel air by pinching tip of condom as it is put on.
- **Explains that once the condom is on the penis, the man or woman should squeeze the teat of the condom and massage the gel, which is inside the condom teat, onto the head of the penis for 15 seconds.**
- Cautions about tearing accidentally with fingernails or rings.
- If the condom starts to roll back up during sex, it should be rolled back down straight away. If the man feels the condom slip or tighten excessively, he should stop and check the condom placement to avoid it

breaking. If the condom comes off the penis, the man should stop and put on a standard (not a Futura Max) condom.

6. Counsels about what to do if condom breaks or slips off during sex.

- Woman should return to clinic to be assessed for emergency contraception.
- Woman should request emergency contraceptive pills within 72 hours (the earlier the better) of unprotected sex or breakage of a condom.

7. Has patient demonstrate and practice putting on condom using the model, banana or fingers.

- Corrects any technique errors.

8. Counsels patient on how to remove penis from vagina with condom intact and without spilling semen.

- Hold on to rim of condom when withdrawing.
- Be careful not to let semen spill into vagina when penis is flaccid.

9. Discusses use of lubricants and what not to use.

- Do not use any of these: petroleum-based products (e.g., Vaseline); mineral, vegetable, or cooking oil; baby oil; margarine or butter.

10. Advises to use a spermicide or water-based lubricant if one is needed.

11. Advises patient to dispose of condoms by burning, burying, or throwing in the latrine.

12. Repeats main condom messages to patient.

- Be sure to have condom on hand before you need it.
- Use a condom with every act of intercourse.
- Do not use a single condom more than once.
- Do not rely on condom if package is damaged, torn, outdated, dry, brittle or sticky.
- **Futura Max condoms are designed to make sex more fun for the couple. Futura Max condoms contain a special gel that makes the man's erection get harder and last longer. This can make sex more pleasurable for the couple.**

13. Provides patient with condoms for two months.

- Multiply patient's expected weekly coital frequency by 9. Give this number of condoms or, if this number is less than 20, give 20 condoms.
- Give 2 standard condoms to use in case the couple has sex more than once within 24 hours.

14. Instructs patient not to share study condoms with anyone but main partner.

- Do not share study condoms with family or friends.

15. Reassures patient that should return at any time for advice or more condoms.

[figure not shown]
VN CSD500 Study
Futura Max™ Information Sheet

Futura Max™ condoms are natural rubber latex condoms which contain Zanifil® gel. They have been shown to maximize hardness by stimulating blood flow within the penis. This can help prevent loss or partial loss of erection, ensuring an intense experience for both you and your partner.

How to use: Use a condom only once. Condoms used more than once are more likely to slip or break and not provide adequate protection. Infections can be passed on in bodily fluids present in the condom after use.

1. Tear open the foil and remove the condom. Be careful with sharp objects such as nails and jewelry. If the carton or foil is damaged, discard and use a condom from an undamaged package.

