5. PSA OUTCOME

The primary study endpoint, detection of PSA in vaginal fluid, is a feasible marker of women's recent exposure to semen from penile-vaginal sex. Forensic research demonstrates that PSA clears from the vagina in a mean of 20-27 hours and is undetectable after 47 hours (Graves 1985; Kamenev 1989). More recently, the protein has been studied for its potential as a semen biomarker for research purposes. Three studies using a controlled design in which women were exposed to specific quantities of their partner's semen in a clinic setting showed high proportions of women tested PSA-positive immediately after exposure (Lawson 1998) followed by a sharp decay curve (Macaluso 1999; Jamshidi 2013). For example, when women were exposed to 1 mL of semen (a volume on the same order of magnitude as the amount in a typical ejaculate) (Cooper 2010), Macaluso et al. found PSA (>1 ng/mL) in 92%, 29% and 3% of women immediately, 24 hours, and 48 hours afterwards, respectively (Macaluso 1999). Given this pattern of clearance from vaginal fluid, observed PSA positivity should be interpreted as the lower bounds of exposure in the past 48 hours. PSA is stable in specimens stored at -70°C after collection (Gallo 2013a). Because it is expressed independently of spermatozoa, PSA is useful for identifying exposure even from men who are vasectomized or otherwise without high levels of spermatozoa. False positive PSA tests from women's endogenous sources of PSA (e.g., serum or urine) are improbable given that the resulting PSA levels would be several orders of magnitude below the established threshold for defining PSA positivity from semen exposure (Gallo 2013b).

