Aho 2010	Guinea	Sex workers	219	84	(38.4)
Anderson 2013	Jamaica	Syndromic STI patients	285 at day 0	24	(8.4)
			286 at day 6	29	(10.1)
Rattray [in press] ^a	Jamaica	HIV-negative, seeking contraception	414 at month 0	103	(24.9)
			401 at month 1	93	(23.2)
			389 at month 3	95	(24.4)
Gallo 2007	Kenya	Sex workers	194 at month 0	30	(15.5)
			183 at month 12	21	(11.8)
Mose 2013	Kenya	In a HIV-discordant relationship	124	3	(10.5)
Gallo 2006	Madagascar	Sex workers	332	126	(38.0)
Minnis 2009^a	Zimbabwe	Sexually-active, HIV-negative	910	196	(21.5)

^a*Two trials of HIV-negative women who were not sex workers or syndromic STI patients*

sizes to account for attrition. Specifically, we assumed that 10% would fail to return after enrollment and, among the 90% remaining in the study, the probability of missing a follow-up visit would be 25%.

Given these assumptions, 500 subjects split equally in two arms will provide us with adequate power (80% for all assumed ranges of values and 90% in many) to detect a clinically meaningful reduction in PSA positivity for most values of rho. For example, at the estimated rho of 0.23, this sample size yields 80% power to detect a RR of approximately 0.61 at alpha level of 0.05. Thus, a total sample of 500 women will ensure adequate power to detect a clinically meaningful change in the frequency of PSA positivity between the study arms.

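### Intervention checklist, item 13: the standard back-up condoms are fixed at 2 while the CSD500 supply scales with coital frequency; scale the back-up too, within the same total

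*Combined protocol and SAP*

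**What the plan says.** Item 4 of the Counseling Checklist: Intervention Arm (Section 16) limits CSD500, labelled Futura Max in the trial: "Couple should not use more than one Futura Max condom within 24 hours. If having sex again within 24 hours, use a standard condom". Section 8.5 carries the same 24-hour limit. Item 5 adds a second use for a standard condom: "If the condom comes off the penis, the man should stop and put on a standard (not a Futura Max) condom".

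Item 13 then sets the two-month supply. For CSD500: "Multiply patient's expected weekly coital frequency by 9. Give this number of condoms or, if this number is less than 20, give 20 condoms". For the back-up: "Give 2 standard condoms to use in case the couple has sex more than once within 24 hours". The control checklist, item 13, uses the same rule for its standard condoms: "Give her this number of condoms or, if this number is less than 20, give her 20 condoms".

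Item 15 of both checklists invites the woman back at any time for more condoms, and the schedule of study procedures allows condom provision at interim visits if needed. Section 8.3 describes follow-up dispensing of the assigned condom only. It mentions free standard condoms for all women at the 6-month visit.

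**The concern.** The plan foresees acts that may not use CSD500 and names the condom to use instead, but does not size the supply of that condom. The CSD500 count rises with coital frequency; the back-up stays at 2. A couple that has used its 2 can skip the act, find another condom, use a second CSD500 too soon, or have unprotected sex. The third option is a repeat nitrate exposure that the checklist is meant to prevent. The fourth is the behaviour that the primary outcome measures. The 2 are used as the need arises, so they are most likely to be gone late in the interval, close to the swab. PSA reflects roughly the last two days: Section 5 reports that one study "found PSA (>1 ng/mL) in 92%, 29% and 3% of women immediately, 24 hours, and 48 hours afterwards".

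The 24-hour limit belongs to the product, and its consequences belong in the intent-to-treat effect. The number 2 is a choice made by the trial.

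**Working it through.** **Inputs from the documents.** Supply of max(20, 9f) assigned condoms per two months, where f is expected acts per week; 2 standard back-ups; at most one CSD500 per 24 hours; control positivity 0.15, rho 0.23, 250 couples per arm, 80% power at RR 0.61 (Section 9.1).

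**Assumptions, because the documents are silent.** Coital frequency, timing of acts, and the share of acts that need a standard condom.

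**Step 1. The plan's power figure** (used only under the objection). Section 9.1 states that "at the estimated rho of 0.23, this sample size yields 80% power to detect a RR of approximately 0.61 at alpha level of 0.05".
- Effective observations per arm without attrition: 250 x 3/(1 + 2 x 0.23) = 513.7.
- Standard error of log RR: sqrt[(0.85/0.15 + 0.9085/0.0915)/513.7] = 0.174.
- Power: Phi(0.494/0.174 - 1.96) = 81.0%.
- With the stated attrition, read as 10% never returning and 25% of the rest missing one visit, there are 438.2 effective observations and power is 74.5%.

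So the 80% is reproduced only without attrition. That is a separate matter and does not affect this point.

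**Step 2. Break-even share.** Two back-ups meet the average need if the share of acts requiring one is at most 2/(9f).

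| Acts per week | 1 | 2 | 3 | 4 | 5 |
|---|---|---|---|---|---|
| Acts in 9 weeks | 9 | 18 | 27 | 36 | 45 |
| Break-even share | 22.2% | 11.1% | 7.4% | 5.6% | 4.4% |

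**Step 3. Chance of needing more than 2 in nine weeks.** Binomial with n = 9f and an assumed share q:

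| Acts per week | q = 2% | q = 5% | q = 10% | q = 20% |
|---|---|---|---|---|
| 2 | 0.5% | 5.8% | 26.6% | 72.9% |
| 3 | 1.6% | 15.0% | 51.5% | 92.8% |
| 4 | 3.5% | 26.8% | 71.2% | 98.4% |

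**Step 4. Need under three timing patterns.** A repeat act is one less than 24 hours after the last CSD500 use. Slip-offs are ignored.
- *Evenly spaced, below 7 acts per week:* need is 0.
- *At most one act per night, clock time varying with SD 1 hour:* simulated mean need per 61-day interval is 0.6, 2.8 and 4.9 at 1, 2.2 and 3 acts per week. It exceeds 2 in 2%, 53% and 89% of intervals.
- *Fully random timing:* a share f/(7 + f) of acts are repeats, so mean need over 9 weeks is 9f²/(7 + f). This is 9/8 = 1.1 at f = 1, 36/9 = 4.0 at f = 2 and 81/10 = 8.1 at f = 3, and it equals 2 at f = 1.36. In simulation over 61 days at 1, 2.2 and 3 acts per week, need exceeds 2 in 11%, 82% and 97% of intervals.

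The nightly pattern is not a true lower case. Nearly all its repeats are consecutive nights a little under 24 hours apart, and repeats under 20 hours average 0.01 per interval. The lower end of the range is about 0.

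**The case against.** **Resupply.** The 2 is the scheduled issue, not a cap. Item 15, interim provision and free standard condoms in routine care all allow more, and item 12 tells couples to keep a condom on hand. This stands, and it limits the problem. It does not remove it: resupply needs a trip that a control couple never makes because of a 24-hour rule, and a repeat act within a day leaves little time for one.

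**A one-arm effect on power.** A reader might infer that the shortfall falls on the intervention arm alone and costs the trial much of its power. At 2.2 acts per week (20/9, where the 20-condom minimum is just used up), suppose 25% of uncovered repeat acts are unprotected and no one is resupplied. This adds 0.62 points (nightly) or 1.30 points (random) of PSA risk:
- 1 - 0.9085 x (1 - 0.0062) = 9.71%, RR 0.65;
- 1 - 0.9085 x (1 - 0.0130) = 10.33%, RR 0.69.

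With power = Phi(2.80 x ln RR/ln 0.61 - 1.96), these give 69% and 56%. But the calculation gives control couples an unlimited supply. They receive max(20, 9f), which is 2 fewer condoms in total than intervention couples, and once they run out every act is uncovered.

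Under the same rule, control stock is 0 at about 35% of visits. With random timing, about 2.1 points are added in the control arm and 1.4 in the intervention arm (a rebuilt model, hence the small difference from 1.30). Then (1 - 0.9085 x 0.986)/(1 - 0.85 x 0.979) = 10.42/16.79 = 0.62, and power is about 77%. With nightly timing RR is about 0.60 and power about 83%, so the direction reverses. At 3 acts per week RR is about 0.66 (random) or 0.62 (nightly), which the same formula turns into about 65% or 77%. Even there, part of the movement comes from uncovered acts added to both arms. The larger losses are not supported.

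**Couples who stop for symptoms.** Section 13.3 says: "Participants will be instructed to stop using the study condoms if either they or their partner experience any of these symptoms". A reader might infer that these couples must live on the 2. The documents do not say so: item 13 gives the 2 for repeat acts, and Section 13.3 refers such couples to standard care.

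**Conclusion.** The mismatch inside the checklist is real: items 4 and 5 require a condom that item 13 does not size. For any couple with more than two such acts in two months, the scheduled issue falls short of the instructions. Consequences are possible unprotected acts and possible second CSD500 uses within 24 hours.

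The size cannot be fixed from the documents. It runs from nothing (spaced acts, about 1 act per week, or a 2% share at 2 to 4 acts per week) to a shortfall in most intervals (about 3 or more acts per week with clustered timing). How many of those acts would be unprotected is unknown; the 25% above is only an illustration. No RR shift or power loss should be attached to the point, and the documents do not show a shortfall confined to one arm. This is an inexpensive improvement to the dispensing rule, not a threat to the primary comparison.

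**What to change.** In item 13 of the intervention checklist, replace the flat 2 as follows. Ask how many acts per week the couple expects within 24 hours of another act (r), multiply by 9, and issue that many standard condoms, minimum 2. Take them out of the couple's present total, max(20, 9f) + 2, and issue the rest as CSD500.

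Example, with r assumed: at f = 3 and r = 0.5, the total is 27 + 2 = 29. Standard condoms are 9 x 0.5 = 4.5, rounded up to 5, which leaves 24 CSD500 for 27 - 4.5 = 22.5 permitted acts. At f = 2 and r = 0 the issue is unchanged: 20 CSD500 and 2 standard.

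The cost is one extra question and one changed line. Total supply does not change, so no imbalance against the control arm is added. Little CSD500 use is lost, because those acts may not use CSD500 anyway. Two limits remain. A couple that overstates its repeat acts may use some standard condoms in place of CSD500, which slightly dilutes the contrast. Slip-offs are not counted separately and still rely on spare back-ups or item 15.
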